#### Deviations that could be considered for exclusion in a PPS analysis

- Treatment errors
- Use of prohibited medication known to influence the primary endpoint
- Key exclusion criteria such as:

- Diagnosis with rapidly progressing NMD such as certain types of Motor Neuron Disease (MND)
- Requirement for continuous mechanical ventilation
- Anticipated requirement for respiratory related hospitalization within the next six months
- History of pneumothorax within past 6 months
- History of hemoptysis requiring embolization within past 12 months
- Home use of OLE therapy within the past 12 months
- Inability or unwillingness to perform OLE therapy or study procedures as required

#### Deviations that should not lead to exclusion of data in a PP analysis

- Patients who violate inclusion/exclusion criteria relating to patient safety
- Issues with documentation of informed consent
- Issues with SAE reporting

Safety analysis set (SS): the set of all patients who have received OLE therapy with The Volara® System.

#### **1.3.2 Protocol Deviations**

Protocol deviations will be summarized for all patients in the FAS pooled together. Patient counts and number of deviations will be presented for minor protocol deviations, major protocol deviations, and for each category of major protocol deviation.

Protocol deviations will also be listed for the FAS. The listing will include patient ID, age, verbatim description of the protocol deviation, the assigned category of protocol deviation, and major/minor status.

#### **1.3.3 Safety Variables**

##### **1.3.3.1 Adverse Events**

The safety profiles are evaluated by:

- Adverse Events (AEs) / Adverse Device Effects (ADE)

- Serious Adverse Events (SAEs) / Serious Adverse Device Effects (SADE)

## 1.4 Interim Analysis

An interim analysis has not been planned for this study.

## 2. ANALYSIS METHODS

### 2.1 General Principles

Unless otherwise specified, summary statistics (n, mean, standard deviation [SD], median, minimum, and maximum values) will be presented for continuous variables. Counts and, if relevant, percentages will be presented for categorical variables.

Unless otherwise specified, data listings will include patient ID, sex, and age at baseline (rounded down to the nearest whole number).

Unless otherwise noted, all analyses will be performed using SAS/Graph® 9.4 software, SAS/STAT® 15.1 software, and BaseSAS® 9.4. Copyright © 2016, SAS Institute Inc. SAS and all other SAS Institute Inc. product or service names are registered trademarks or trademarks of SAS Institute Inc., Cary, NC, USA. All Rights Reserved

Unless otherwise specified, the estimated mean and median for a set of values will be displayed to 1 more significant digit than the original values, standard deviations will be displayed to 2 more significant digits, and minimum and maximum values will be displayed with the same number of significant digits as the original values. If an original value has more than 2 decimal places, the significant digits will be counted as if there are 2 decimal places. All percentages will be displayed with 1 decimal place unless more decimal places are needed to show 1 significant digit (i.e., a percentage of 0.01 will be shown as 0.01 as opposed to 0.0).

#### 2.1.1 Definition of baseline

Unless otherwise specified, baseline is defined as the values collected at the baseline visit. The value closest to the start of treatment will be used for baseline if multiple values are available.

Change from baseline variables will be calculated as the post-treatment value minus the value at baseline.

### 2.1.2 Study Periods

The study periods include the 12-month pre-treatment historical control period, 6-month pre-treatment historical control period, and the active treatment period.

The active treatment period begins once a subject has started therapy with The Volara® System.

### 2.1.3 Visit Windows

The study visits for the active treatment period can be obtained from the eCRF and need not be derived programmatically. The visits will be displayed as: Baseline, 1-month, 2-month, 3-month, 4-month, 5-month, 6-month.

Results from unscheduled study visits will not be included in table summaries. These values will only be presented in the listings.

### 2.1.4 Completion and Discontinuation

A patient is considered to have completed the study when he/she ceases active participation in the study because the patient has, or is presumed to have, completed all study procedures according with the protocol (with or without protocol deviations). Any other cases are classified as discontinuation.

Reasons for completion/discontinuation will be reported on the Completion/Discontinuation electronic case report form (eCRF), including:

- Protocol Violation
- Withdraw Consent
- Lost to Follow-Up
- Adverse Device Effect
- Other

Regardless of the reason, all data available for the patient up to the time of completion/discontinuation should be recorded on the appropriate eCRF.

## 2.2 Patient Disposition

Patient disposition will be summarized and will include:

- Number of patients screened
- Number of patients who screen fail. These patients will also be summarized by primary reason for screen failure from the study. The percentage associated with each reason will have the total number of patients who screen fail as the denominator.
- Number of patients enrolled
- Number of patients included in chart review for 12-month pre-treatment period
- Number of patients eligible for treatment
- Number of patients treated with study device
- Number of patients in the FAS
- Number of patients in the PPS
- Number of patients in the SS
- Number of patients who completed the study
- Number of patients who discontinued (withdrew early) from the study. These patients will also be summarized by primary reason for withdrawal from the study. The percentages associated with each reason for early withdrawal will have the total number of patients who withdrew early as the denominator.

A listing of all patients enrolled in the study will be created including patient ID, age, sex, completion status, reason for discontinuation (if applicable), and the number of days that the patient remained in the study. The number of days the patient was in the study will be calculated using the following:

$$(Date \text{ of } Study \text{ Completion/Discontinuation} - Date \text{ of } Enrollment) + 1$$

## 2.3 Demographics and Other Baseline Characteristics

Demographics and other baseline characteristics will be summarized descriptively for the FAS population. A listing will also be provided for this population.

### 2.3.1 Demographics

Demographics (age, race, ethnicity, sex) will be summarized descriptively.

### 2.3.2 Other Baseline Characteristics

Baseline characteristics including height, weight, and BMI will be summarized descriptively.

### 2.3.3 Medical History

All neuromuscular disease and pulmonary disease medical history will be listed.

### 2.3.4 Concomitant Medications

All pulmonary and respiratory related concomitant medications will be listed.

## 2.4 Endpoint Analyses

### 2.4.1 Primary Endpoint

The primary endpoint analysis will be carried out on the FAS with a supportive analysis performed on the PPS.

#### 2.4.1.1 Derivation of Primary Endpoint

Exacerbations of pulmonary disease are defined as changes in respiratory status requiring intervention. Documentation of pneumonia or respiratory infection, change in chest x-ray, changes in requirement for respiratory support necessitating any of the interventions below will be considered an exacerbation of pulmonary disease:

- Hospitalization
- ED Visit
- Unscheduled Antibiotics for Respiratory Infection
- Unscheduled outpatient visit

Pulmonary exacerbation events that occurred during the 12-month pre-treatment period and the active treatment period will be recorded in the data. Pulmonary exacerbation events that occurred prior to the Volara® start date occurred in the pre-treatment period. Pulmonary exacerbation events that occurred on or after the Volara® start date occurred in the active treatment period. The paired difference in pulmonary exacerbation events for each subject will be calculated as follows:

$$\begin{aligned} & \text{Number of pulmonary exacerbations in active treatment period} \\ & - \text{Number of pulmonary exacerbations in 6 months prior to treatment start} \end{aligned}$$

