3.3.4.1 Primary Endpoint(s):**• Frequency of exacerbations of pulmonary disease**

Exacerbations of pulmonary disease are defined as changes in respiratory status requiring intervention. Documentation of pneumonia or respiratory infection, change in chest x-ray, changes in requirement for respiratory support necessitating any of the interventions below will be considered an exacerbation of pulmonary disease:

- Hospitalization
- Emergency Department (ED) Visit

PROTOCOL TITLE**Evaluation of Oscillation and Lung Expansion (OLE) using The Volara® System for treatment of respiratory complications in patients with neuromuscular disease in the home setting****Final Protocol****Protocol Number:** CR-RR-2020-005**Date:** 11May2022

- Antibiotics (oral, intravenous, or nebulized)
- Unscheduled Outpatient Clinic Visit

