3.3.4 Study Exit Documentation

Study exit data is collected to document the reason participation in the study ended. Reasons for exit from the study include:

- **Completion of the study**
- **Subject inability to tolerate therapy**
- **Subject withdrawal**
This may be voluntary withdrawal on the part of the subject or subject caregiver or withdrawal by investigator for subjects deemed unfit for or unsafe to continue the trial
- **Subject death**

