5.6 Subject Death

All subject deaths are to be documented and reported to the sponsor within 72 hours after becoming aware of the event.

PROTOCOL TITLE**Evaluation of Oscillation and Lung Expansion (OLE) using The Volara® System for treatment of respiratory complications in patients with neuromuscular disease in the home setting**

Final Protocol

Protocol Number: CR-RR-2020-005**Date:** 11May2022**5.7 Complaint or Device Deficiency Definition**

A complaint is defined as any written, electronic or oral communication that alleges deficiencies related to the identity, quality, durability, reliability, safety, effectiveness, or performance of the device after its release for distribution (21 CFR 820.3(b)).

Any device complaint and/or allegation of injury shall be reviewed, evaluated, and investigated by Hillrom Post Market Surveillance and reported to the appropriate Health Authority per current regulations. The Investigators are responsible for informing the Institutional Review Boards, as per their guidelines.

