### 1.1 Study Objectives and Endpoints

The objective of the study is the evaluation of the impact of Oscillation and Lung Expansion (OLE) therapy to treat respiratory complications of neuromuscular disease in patients.

Primary Endpoint:

- Frequency of exacerbations of pulmonary disease requiring medical intervention (e. g. one or more of the following):
  - Hospitalization
  - Emergency Department (ED) Visit
  - Unscheduled Antibiotics for Respiratory Infection
  - Unscheduled outpatient visit

Secondary Endpoints:

- Pulmonary function tests
  - Slow Vital Capacity (SVC)
  - Peak Cough Flow (PCF)
  - Resting Oxygen Saturation (SPO2)
  - Maximal Inspiratory Pressure (MIP)
- Number of hospital admissions
- Total hospital length of stay
- Number of intensive care unit (ICU) admissions

- Total ICU length of stay
- Number of outpatient visits for pulmonary complication (Unscheduled Physician's office, Urgent Care Visits, ED visits)
- Number of antibiotic use days during episodes of pulmonary exacerbation
  - IV (intravenous) antibiotic days
  - Oral antibiotic days
  - Nebulized antibiotic days
- Quality of Life (QOL) Assessment
- Patient/caregiver satisfaction with therapy

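### The primary analysis has no rule for death: a respiratory death without a listed intervention adds no event, shortens the count, and can score as a reduction.

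*SAP*

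**What the plan says.** The protocol (3.3.4.1) sets the frame: "Exacerbations of pulmonary disease are defined as changes in respiratory status requiring intervention". SAP 2.4.1.1 repeats it and ties a counted event to four interventions: "changes in requirement for respiratory support necessitating any of the interventions below will be considered an exacerbation of pulmonary disease". Death is not among them. The endpoint list in SAP 1.1 is slightly looser, "Frequency of exacerbations of pulmonary disease requiring medical intervention (e. g. one or more of the following", but still requires a medical intervention.

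The score for each patient is a difference of raw counts: "Number of pulmonary exacerbations in active treatment period" minus "Number of pulmonary exacerbations in 6 months prior to treatment start". There is no exposure term. SAP 2.1.2 fixes when the active period starts, "The active treatment period begins once a subject has started therapy with The Volara® System", but gives no end date, no minimum length and no rule for death.

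The FAS (SAP 1.3.1) needs one event in the prior 12 months and one Volara treatment. SAP 2.6.1 uses data up to dropout and imputes nothing.

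The plan does foresee deaths. The protocol's exit reasons (3.3.4 Study Exit Documentation) include "Subject death", and Protocol 5.6 says: "All subject deaths are to be documented and reported to the sponsor within 72 hours after becoming aware of the event". SAP 2.5.1.2 and Table 14.3.1.1.7 summarise treatment-emergent AEs leading to death. The discontinuation reasons in SAP 2.1.4 do not name death, so it would fall under the category Other. No section says how a death enters the primary endpoint.

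**The concern.** Two gaps meet in the same patient. The event definition can miss the death itself, and the raw count stops on the day of death while the control count covers a full six months. Both lower the active-period count.

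The control window cannot contain a death, because every FAS patient must be alive to receive a first treatment.

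At stake are the mean paired difference and its 95% CI. These are the study's main result, and the protocol (Comparison of Pre-treatment and Active Treatment Periods) wants to relate them to use of the device. In a neuromuscular population, an endpoint on which the worst respiratory outcome can look like an improvement needs at least an explicit rule and a check.

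**Working it through.** The documents give no event rate, SD, death rate or power figure, and the sample of about 70 is one of convenience. There is therefore no stated figure to reproduce. The inputs from the documents are n=70 (SAP 1.2.2), the paired-difference formula (SAP 2.4.1.1), the FAS rule (SAP 1.3.1), the entry rule of one event in 6 months or two in 12 (Protocol 3.2.1), and the 95% CI for the mean paired difference (SAP 2.4.1.2). Everything else below is assumed.

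**Step 1. Score of one patient who dies of a respiratory cause with no listed intervention.** Score = on-treatment count at death - six-month control count.

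| Control count | On-treatment events before death | SAP score | Score if the death counts as one event |
|---|---|---|---|
| 0 | 0 | 0 | +1 |
| 1 | 0 | -1 | 0 |
| 2 | 0 | -2 | -1 |
| 3 | 0 | -3 | -2 |
| 1 | 1 | 0 | +1 |
| 1 | 2 | +1 | +2 |

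With no on-treatment event, the score is the lowest that patient could reach. A control count of 0 is possible because entry can rest on two events in months 7 to 12 before treatment.

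**Step 2. How often a death scores as a reduction.** This was simulated with stable Poisson rates of 1, 1.5, 2 and 3 per six months, the entry rule applied, and no device effect.
- Control count of 0: 4% to 13% of eligible patients.
- Scored as a reduction: 79-88% for death at month 1, 63-69% at month 3 and 49-53% at month 5.
- Six-month survivors with no true change: 42-47%.
- Rate 1.5, death at month 3: counting the death as an event lowers the share from 63% to 33%, not to zero. The rest reflects the shortened count and chance.

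**Step 3. Effect on the mean at n=70.**
- Counting a death as one event: 1/70 = 0.014 per death; 3/70 = 0.043 for three.
- Replacing -2 by an assumed worst score of +3: (3 + 2)/70 = 0.071 per death; 15/70 = 0.21 for three.
- CI half-width, with independent Poisson counts of mean 1.5 in each period: t(0.975, 69) × √(2 × 1.5)/√70 = 0.413.
- Ratios for three deaths: 0.043/0.413 = 10%; 0.21/0.413 = about half.

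**Step 4. Shortened count and uncounted death together, relative to full follow-up.** Shift = -(d/70) × [rate × (1 - t/6) + 1], for d deaths at month t. With rate 1.5 and t = 3, each death gives -(1.5 × 0.5 + 1)/70 = -0.025, and three give -0.075. Of the 0.025, 0.75/70 = 0.011 is lost follow-up and 0.014 is the uncounted death. Over rates 1 to 3, one to seven deaths and death at month 1 or 3, the shift runs from -0.02 to -0.35.

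**The case against.** A reader might infer that any death on the device scores as a reduction. The documents do not support that. The control count must exceed the on-treatment count at death, and the entry and FAS rules admit patients whose six-month control count is 0. A fatal episode that involved one of the four interventions is counted. Only deaths without one escape the definition, although every death shortens the count.

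A reader might also take the 0.21 for three deaths as the size of the problem. It belongs only to an assumed score of +3 with a control count of 2. It also takes all three deaths to be respiratory and without a listed intervention. Frequent deaths cannot be presumed: Protocol 3.2.2 excludes rapidly progressing disease, continuous ventilation and anticipated respiratory hospitalization.

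The case for leaving the plan alone is that this is a descriptive pilot without hypothesis tests, that deaths appear in the safety output, and that adding death to the endpoint would change the protocol's definition and count an event possible in only one period. The last argument stands, and it is why the primary definition should stay. The first two stand only in part. No decision rule is affected, but safety tables do not correct the primary mean or CI. Capture there is also uncertain, since Protocol 5.0 makes only adverse device effects and device complaints reportable. A death judged unrelated reaches the sponsor under Protocol 5.6, but need not reach an AE table.

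Most of the shortened count is a follow-up problem that person-time would address. In a pooled rate, two event-free months carry only two months of weight. Person-time does not add the missing event, however.

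**Conclusion.** The point holds in a limited form. The plan has no rule for death in its primary endpoint. What it does say implies that a patient who dies stays in the paired difference with a shortened count, and that a respiratory death without a listed intervention adds no event. Relative to full follow-up, this can only lower the patient's score, so the bias favours the device.

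Inclusion is inferred from SAP 1.3.1 and 2.6.1; no sentence states it. If such patients were treated as missing, they would leave n and not score at all, so the SAP should say which applies.

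The missing event itself is worth little per death and is small against the CI half-width for a few deaths. It becomes material only with more deaths or a deliberately severe score. All sizes rest on assumed rates and death counts. The correction is worth making because it is cheap and the direction of the bias is known.

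**What to change.** Keep the primary definition and make these changes:

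- **SAP 2.4.1.1:** state that FAS patients who die in the active period are included in the paired difference, with events counted up to death.
- **SAP 2.4.1.2:** add a sensitivity analysis with two parts: (a) a respiratory death in the active period counts as one event, whether or not a listed intervention occurred; (b) each patient who died receives the worst paired difference observed in the analysis set.
- **Tables 14.2.1.1 and 14.2.1.2:** show the number of deaths, respiratory and all-cause, beneath the results.
- **SAP 2.1.4:** list death as a discontinuation reason, to match the protocol's exit reasons.
- **Early exit for any reason:** handle separately with an exposure-adjusted analysis of events per person-time. This addresses shortened follow-up but does not replace (a) and (b).

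The death-specific changes cost SAP wording, one extra analysis and possibly a cause-of-death field on the exit form. Parts (a) and (b) can only make the result less favourable. The control period cannot contain deaths, so (a) and (b) belong in a sensitivity analysis and not in the primary definition.

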| Methods: | 
After enrollment, baseline data including demographics, pulmonary related medical history including acute respiratory-related hospitalizations, ED visits and unscheduled physician office visits, that occurred during the 12 months prior to OLE therapy initiation, will be documented. Pulmonary function tests (PFTs) will be performed. Quality of Life measures, adherence to therapy and satisfaction with therapy data will be collected.
 
Enrolled patients will be started on OLE therapy with The Volara® System. The device will be used within the approved product labeling. This will be the primary airway clearance devices for these patients during the 6 months of the active-treatment study period. Cough therapy such as mechanical insufflation exsufflation (MIE) therapy will be continued if currently prescribed. Other treatments such as high-frequency chest wall oscillation (HFCWO) or chest physiotherapy (CPT) will not be performed during the active treatment period.
 
Following enrollment, completion of a baseline visit, and initiation of OLE therapy, subjects will be seen for 3 follow-up visits. Medical records will be reviewed for the 6-month active treatment study period to document the occurrence of acute respiratory events, documentation will include respiratory related interventions including: number of hospitalizations and hospitalization days, time to first hospitalization, number of courses of antibiotics for respiratory complications, number of ICU admissions and ICU days, and number of outpatient visits (unscheduled Physician's office visit, Urgent Care Visits, ED visits). Respiratory support requirements during the active treatment period will also be documented.
 
The following tests/procedures will be performed/assessed during the active treatment period:
 
• Pulmonary function will be assessed to obtain SVC, PCF, SPO2, and MIP.• A quality-of-life measure will be administered• Adherence to the prescribed therapy regimen will be assessed using the internal therapy log in The Volara® System. |
|-----------------|---|

PROTOCOL TITLE

Evaluation of Oscillation and Lung Expansion (OLE) using The Volara® System for treatment of respiratory complications in patients with neuromuscular disease in the home setting

Final Protocol

Protocol Number: CR-RR-2020-005

Date: 11May2022

| | |
|-----------------------------|--|

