3.3 Study Observations, Procedures and Evaluation Criteria

The study is a decentralized trial. All study visits required for the completion of the trial will occur in the home or will be done virtually. Eligible subjects will be pediatric and adult patients ages 5 – 80 who are able to perform OLE therapy using a mouthpiece, mask, or trach adaptor and who meet all inclusion and none of the exclusion criteria. Informed consent (and assent if minor subject) will be obtained prior to enrollment in the study. Demographic and medical history data will be collected from the medical record of each subject at the time of enrollment.

3.3.1 Informed Consent:

Informed consent (and assent if minor subject) will be obtained from the patient or legally authorized representative prior to enrollment in the study. Informed consent will be obtained by the principal investigator or his/her representative.

3.3.2 Selection Criteria:

Inclusion and exclusion criteria will be reviewed and documented for all study subjects (criteria are described in section 3.2 above).

3.3.3 Study Visits and Data Collection Procedures:

All study subjects will complete a virtual home baseline study visit for initiation of the trial and enrollment into the study. Following the baseline visit, each study subject will complete three follow-up visits. The first follow-up visit will be approximately one month after initiating therapy

PROTOCOL TITLE

Evaluation of Oscillation and Lung Expansion (OLE) using The Volara® System for treatment of respiratory complications in patients with neuromuscular disease in the home setting

Final Protocol

Protocol Number: CR-RR-2020-005**Date:** 11May2022

and will occur virtually or by phone. Follow-up visits two and three will be done virtually and will occur approximately three months and six months after initiation of OLE therapy. Pulmonary function measures will be collected at baseline and at the end of each month of therapy during the active treatment period. Study Visits and procedures for data collection is described below.

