3.3.3.5 Home Training on The Volara® System: A Hillrom designated trainer will set up the device and review operation and treatment protocol at the time the device is delivered. Study subjects and caregivers will be instructed to use the device as their primary airway clearance and lung expansion therapy for a period of six months. Hillrom training staff will follow up with each Volara user according to the standard device placement and follow-up program.

3.3.3.6 Adherence Documentation: During the six-month follow-up period, adherence to the daily prescribed therapy regimen will be assessed. The Volara® System logs therapy details for each therapy completed, including the total time of therapy, the number of stages completed, the total time in CPEP mode, total time in CHFO mode and peak pressures achieved in each mode. Adherence data logs will be downloaded on a regular basis during the active treatment period.

3.3.3.8 One-month Virtual Study Visit: A one-month study visit with each study subject will be conducted virtually. Visits will be completed +/- 3 days from the one-month scheduled visit date. During this visit, the following procedures and assessments will be conducted:

- Review of study procedures with subject/caregiver
- Review of current respiratory status, respiratory treatments, and medications
- Documentation of patient/caregiver reported exacerbations and medical interventions for the prior period (run-in and first month of Volara therapy)
- Documentation of any Adverse Device Effects that the subject experienced during the follow-up period
- Completion of QOL questionnaire
- Completion of Patient/Caregiver Satisfaction survey

3.3.3.9 Three-month and Six-month Virtual Study Visits: Three-month and six-month study visits with each study subject will be conducted virtually by study staff. Visits will be completed

PROTOCOL TITLE

Evaluation of Oscillation and Lung Expansion (OLE) using The Volara® System for treatment of respiratory complications in patients with neuromuscular disease in the home setting

Final Protocol

Protocol Number: CR-RR-2020-005**Date:** 11May2022

+/- 3 days from the one-month scheduled visit date. During these visits, the following procedures and assessments will be conducted:

- Review of study procedures with subject/caregiver
- Review of current respiratory status, respiratory treatments, and medications

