#### 2.4.1.2 Analysis of Primary Endpoint

The primary endpoint of the study, frequency of exacerbations of pulmonary disease requiring medical intervention, will be analyzed descriptively by study period (active treatment and 6-month pre-treatment) using n, mean, standard deviation, minimum, median, and maximum. The paired difference in the frequency of exacerbations of pulmonary disease requiring medical intervention between study periods (active treatment period - 6-month pre-treatment historical control period) will also be analyzed descriptively with n, mean, standard deviation, minimum, median, maximum and 95% two-sided confidence interval (CIs) for the mean paired difference. All pulmonary exacerbation events that occurred in the 12-month pre-treatment period and the active treatment period will be listed.

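### The SAP gives the active treatment period a start but no end, so its raw exacerbation count can cover a different length of time from the fixed six-month control

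*SAP*

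**What the plan says.** SAP 2.1.2 names three study periods. The two historical ones carry a length (12 and 6 months). For the third it says only that "The active treatment period begins once a subject has started therapy with The Volara® System". The primary derivation in SAP 2.4.1.1 repeats the open end: "Pulmonary exacerbation events that occurred on or after the Volara® start date occurred in the active treatment period". From that count it subtracts the "Number of pulmonary exacerbations in 6 months prior to treatment start". SAP 2.4.1.2 then reports the mean of these differences with a "95% two-sided confidence interval (CIs) for the mean paired difference". No observed time enters the calculation.

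Two other SAP sections determine which data reach the count. Section 2.1.4 has data recorded up to completion or discontinuation and defines completion by procedures done, not by a day number. Section 2.6.1 uses everything collected up to dropout and imputes nothing. Under section 1.3.1, a single Volara treatment meets the exposure condition for the full analysis set.

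The protocol does state a length. Its synopsis says "Medical records will be reviewed for the 6-month active treatment study period to document the occurrence of acute respiratory events". Section 3.3.3.5 has subjects "use the device as their primary airway clearance and lung expansion therapy for a period of six months". Section 3.3.3 places the later visits "approximately three months and six months after initiation of OLE therapy".

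**The concern.** A difference of raw counts is interpretable only if both counts cover the same length of time. Here the control side is fixed and the active side runs from the first treatment to wherever the recorded data stop. A programmer who follows SAP 2.4.1.1 to the letter counts an event on day 200 if it is in the database. One who reads the protocol's six months into the SAP leaves it out. Both have followed a governing document, and they get different primary results.

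The six health-care-use endpoints in SAP 2.4.2.2 to 2.4.2.7 are also summarised as active period against six months pre-treatment, so they inherit the same ambiguity. The study is descriptive, and Protocol 3.5.1 hopes the data will help define effect size and variability for later studies. The estimate is therefore its main product.

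**Working it through.** The plan has no figure of its own to reproduce: the sample of about 70 is a convenience sample, with no event rate, SD or dropout rate stated. The check is window arithmetic.

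**Inputs from the documents.** Control window: 6 months. Participation: about 7 months (Protocol Synopsis). Run-in before therapy: 2 to 4 weeks (Protocol 3.3.3.4). N: about 70.

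**Assumptions, not in the documents.** A constant rate λ of 1 to 2 events per six months, no device effect, SD of the paired difference 1 to 2, and 10 to 30% dropout. One month is 365.25/12 = 30.44 days, so six months is 182.6 days and seven months is 213.1 days.

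**Formula.** With T months counted on device, the expected paired difference due to window length alone is λ × (T/6 − 1).

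**Step 1: plausible overrun.** Time on device is participation minus run-in.
- 4-week run-in: 213.1 − 28 = 185.1 days, an overrun of 185.1 − 182.6, about 2 days.
- 2-week run-in: 213.1 − 14 = 199.1 days, an overrun of 199.1 − 182.6, about 16 days.

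Conversely, six months plus 2 to 4 weeks is 6.5 to 6.9 months, which also fits a description of about seven months. The overrun may therefore be nil.

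**Step 2: extra events per overrunning patient**, λ × overrun/182.6.

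| Overrun | λ = 1 | λ = 2 |
|---|---|---|
| 2.4 days | +0.01 | +0.03 |
| 16.4 days | +0.09 | +0.18 |

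The shift in the study mean is this value times the share of patients who overrun.

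**Step 3: shortfall from early leavers.** With a share d leaving at month t, mean T = 6(1 − d) + d·t.

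| Dropout | Leaving at | Mean T (months) | Change in time | Difference, λ = 1 to 2 |
|---|---|---|---|---|
| 10% | month 3 | 5.7 | −5% | −0.05 to −0.10 |
| 20% | month 3 | 5.4 | −10% | −0.10 to −0.20 |
| 30% | month 3 | 5.1 | −15% | −0.15 to −0.30 |
| 10% | month 1 | 5.5 | −8% | −0.08 to −0.17 |
| 20% | month 1 | 5.0 | −17% | −0.17 to −0.33 |
| 30% | month 1 | 4.5 | −25% | −0.25 to −0.50 |

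**Step 4: scale.** The 95% CI half-width is t(0.975, 69) × SD/√70 = 0.24, 0.36 or 0.48 for SD 1, 1.5 or 2. Even if every patient overran by 16 days at λ = 2, the shift (0.18) would be smaller than the narrowest of these. The heavier dropout cases reach the same order as the half-width.

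**Step 5: what each remedy does.** A cap sets T ≤ 6, which removes Step 2 and leaves Step 3. Dividing by observed time gives (λT/6)/T = λ/6, which does not depend on T, so both go under a constant rate.

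**The case against.** The strongest reply is that the protocol already fixes the period. Record review, device use and follow-up are each described as six months, and Protocol Table 1 puts both the active-period record documentation and the exit form in the six-month column. The SAP says it is based on that protocol. The study is descriptive, and all events are listed, so a late one would be visible. This stands in part: a reader might infer from the SAP alone that nothing bounds the active period, and the protocol does not support that. What is missing is a counting rule in the SAP, and a listing does not correct a mean and interval already computed from the wrong window.

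A reader might also link the open end to Protocol 3.3.3.9, which sets the three- and six-month visits at plus or minus "3 days from the one-month scheduled visit date. During these visits, the following procedures and assessments will be conducted". Read literally, this puts them at about 27 to 33 days, in conflict with section 3.3.3. The wording looks carried over from the one-month visit. No passage says the six-month visit closes the event count, so this is a separate inconsistency and not the cause of the open window.

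Finally, one might suppose overruns of a month or more, or suspect that the open end flatters the device. Nominal participation less the run-in does not imply overruns of that size, and extra counting time adds active-period events, which works against the device.

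**Conclusion.** The point holds as a gap in the SAP. The active period has no operational end, raw counts are differenced, and the windows can be unequal. On the documents' own timings the overrun is small: about 2 to 16 days, or 0.01 to 0.18 events per overrunning patient at an assumed 1 to 2 events per six months. The documents do not show how many patients would overrun. The opposite mismatch, from patients who leave early, favours the device and is probably the larger: 0.05 to 0.30 events on the mean for an assumed 10 to 30% leaving at month 3.

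These figures isolate window length under a constant rate. They do not predict the observed pre-post difference, because patients are selected on recent exacerbations and the difference would not be expected to be zero even without a device effect. The gap should be closed, but it does not invalidate the study.

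**What to change.** - **SAP 2.1.2 and 2.4.1.1:** end the active period, for counting, at six months from the Volara start date or at study exit if earlier. For example, count day 1 (start date) to day 182, and define the control as the 182 days ending the day before start. Another definition of six months would serve, provided both sides use the same number of days.
- **SAP 2.4.2.2 to 2.4.2.7:** apply the same two windows, and state how hospital, ICU or antibiotic days that cross a boundary are split. List later events without counting them.
- **SAP 2.4.1.2:** report observed days per patient and, beside the paired difference, the exacerbation rate per observed time in each period (total events over total days). Protocol 3.5.2 already speaks of comparing a rate. This corrects for shorter observation, but not for early leavers having a different underlying rate.
- **Protocol 3.3.3 and 3.3.3.9, separately:** reconcile the visit timing, for instance by anchoring each visit to its own scheduled date counted from OLE initiation.

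The cost is a few sentences, one date condition and one extra summary. A few events after day 182 leave the count but stay in the listings. SAP 2.6.2 describes the study in the past tense, so the protocol correction may now have little effect on conduct; the SAP change remains useful for the analysis.
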